2.7.6 Immunogenicity

Number and percentage of subjects with treatment-induced transient and persistent ADA and no treatment-induced ADA will be summarized. Listing will be provided.

Treatment induced ADA will be defined as a negative ADA sample at baseline and at least one positive ADA sample post-baseline. Persistent will be defined as negative ADA at baseline and confirmed positive ADA on 2 or more timepoints where the first and last were separated by a period of at least 16 weeks or positive ADA at the last timepoint or at a timepoint less than 16 weeks before an ADA negative last sample. Transient will be defined as treatment-induced ADA detected at only 1 time point post-baseline, or 2 or more sampling time points where the first and last ADA-positive samples are separated by a period less than 16 weeks, and the subject's last sampling time point is ADA-negative.

In addition, further ADA details will be assessed and will be listed in a separate ADA report. If applicable, additional analyses may be conducted.

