Approximately 12 participants who meet the inclusion/exclusion criteria will be randomized in a 2:1 ratio to receive either inclisiran sodium 300 mg s.c. or placebo on Day 1 (baseline). A second and third dose of inclisiran or placebo will be given on Day 90 and Day 270, respectively. The primary endpoint will be measured at Day 330.

[figure not shown]
Participants initially randomized to placebo will transition to inclisiran starting on Day 360 and the study will then change to an open-label, single arm follow-up period of inclisiran sodium 300 mg s.c. (Part 2). In order to maintain the blind for Part 1 of the study, on the "switch" day (Day 360), participants randomized to placebo in Part 1 will receive blinded inclisiran, while participants randomized to inclisiran in Part 1 will receive blinded placebo. All participants will receive subsequent doses of open-label inclisiran on Day 450 and Day 630.

The EOS visit will be on Day 720. In addition, a safety follow-up call will be conducted 30 days after the last study visit or 90 days after the last administration of study drug, whatever is longer.

Inclisiran and placebo will be administered exclusively by a health care provider at the study site. Participants will be observed in the clinic for at least 4 hours post injection on Day 1 and Day 360 (i.e. first dosing of inclisiran) and for at least 30 minutes post injection for all other dosing visits before being discharged.

Participants on a documented regimen of LDL-apheresis will be allowed to continue their same regimen during the study, if needed. The apheresis schedule is not allowed to change during Part 1 (Year 1) of the study (including the screening/run-in period). The apheresis schedule must also allow that an apheresis coincides with each study visit. Study drug is to be administered the same day, after completion of apheresis (the next scheduled apheresis should not occur within 72 hours after an administration of study drug). Blood samples for LDL-C (and other laboratory assessments of efficacy and safety) must be obtained immediately before the scheduled apheresis treatment at each applicable study visit (including screening and baseline (Day 1)).

Figure 3-1 Study Design

* Primary endpoint assessed at Day 330. # "Switch Day": Participants randomized to placebo in Part 1 will start to receive inclisiran on Day 360. Participants randomized to inclisiran in Part 1 will receive placebo on Day 360 only to maintain the blind for Part 1.

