8.4.1.1 Anti-drug antibodies

Serum samples for the analysis of formation of ADA will be collected at the time points detailed in the Assessment Schedule ([Table 8-1](#)).

On Day 1, ADA serum samples will be collected prior to injection and 4 hours after injection. At all other visits, one sample only will be collected.

The results from ADA after the first administration of study drug until the Day 360 visit must be blinded to participants, investigator staff, persons performing the assessments, and the CTT.

Instructions to be followed regarding sample collection, numbering, processing and shipment are outlined in a Laboratory Manual.

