12.4.2 Statistical model, hypothesis, and method of analysis

The primary analysis will summarize change from baseline using summary statistics to characterize change from baseline in LDL-C by treatment group and the difference between treatment groups at the Day 330 time point. No formal hypothesis testing is planned.

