12.8 Sample size calculation

12.8.1 Primary endpoint(s)

The sample size for this study was selected based on feasibility.

13 Ethical considerations and administrative procedures

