2.1.1 General definitions

Study Day

Study day will be defined as the number of days since the date of first dose of double-blind treatment. The date of first dose of double-blind treatment will be defined as Day 1 and the day before the first dose of study drug will be defined as Day -1.

Therefore, for a particular date, study day will be calculated as follows:

For dates on or after the first date of double-blind treatment,

Study day = Assessment date – Date of first dose of double-blind treatment + 1;

For dates prior to the first date of double-blind treatment,

Study day = Assessment date – Date of first dose of double-blind treatment.

In case, participant has been randomized but has not received double-blind treatment then randomization visit day will be considered as Day 1.

Baseline definition

In general, for both Part 1 and Part 2, baseline value is defined as the last measurement collected on or prior to the first dose of double-blind treatment.

Post-baseline measurement

Post-baseline values are defined as those measurements that were collected after the first dose of double-blind treatment.

When change from baseline is of interest the following formula will be used for each scheduled visit and time-point where baseline and post-baseline values are both available:

Absolute change from baseline = post-baseline value – baseline value.

Percent change from baseline = (post-baseline value – baseline value) / baseline value*100.

LDL-C to be used in analysis

The endpoints involving LDL-C will use the beta quantification (ultracentrifugation) LDL-C for all subjects. In cases where beta quantification (ultracentrifugation) LDL-C values are missing and calculated LDL-C is available, the calculated LDL-C will be used for analysis purposes.

VLDL-C

The endpoints involving VLDL-C will use the beta quantification (ultracentrifugation) VLDL-C for all subjects. In cases where beta quantification (ultracentrifugation) VLDL-C values are missing and calculated VLDL-C is available, the calculated VLDL-C will be used for analysis purposes.

Discontinuation visit mapping

For patients who discontinued the study and come to site for an early exit (EE) visit, the EE visit will be mapped to the next scheduled visit. The mapping details can be found as below:

Table 2-1 Visit mapping

Status	Last attended scheduled visit prior to EE		Mapped visit for EE	
Visit day	Visit name	Visit day	Visit name	Visit day
Discontinued (Early exit)	1	Day 1	90	Day 90

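### By the SAP's definitions the 4-hour Day 1 sample counts towards treatment-induced and persistent ADA, and the transient and persistent classes need tightening for this sampling schedule

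*SAP*

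**What the plan says.** - Protocol 8.4.1.1: "On Day 1, ADA serum samples will be collected prior to injection and 4 hours after injection". Each later ADA visit has one sample. Table 8-1 places ADA at Days 1, 150, 330, 510 and 720.
- SAP 2.1.1: "Post-baseline values are defined as those measurements that were collected after the first dose of double-blind treatment". No minimum interval after dosing is set.
- SAP 2.7.3 counts ADA among the laboratory data and takes the last value before the first double-blind dose as baseline.
- SAP 2.7.6: "Treatment induced ADA will be defined as a negative ADA sample at baseline and at least one positive ADA sample post-baseline".
- SAP 2.7.6 calls a response persistent in any of three cases: confirmed positives at two or more time points at least 16 weeks apart; a positive last sample; or a positive less than 16 weeks before a negative last sample.
- SAP 2.7.6 on the other class: "Transient will be defined as treatment-induced ADA detected at only 1 time point post-baseline", or at several time points spanning less than 16 weeks. It closes with the condition that the last sample is negative.
- ADA is part of the safety endpoint in Protocol Table 2-1. SAP 2.7.6 reports counts and percentages with a listing.

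**The concern.** Three rules, each sensible alone, combine badly. The general post-baseline definition takes in the 4-hour sample, and nothing in SAP 2.7.6 takes it out again. A positive there is labelled as induced by a treatment given 4 hours earlier. It can also act as the first of two positives and turn an isolated later finding into a persistent response. The same happens in the placebo arm, which receives no inclisiran before Day 360.

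Separately, the 16-week cut-off is shorter than every gap between scheduled ADA samples. The label transient then suggests a short duration that the data cannot show. The two class definitions also have no precedence rule for a participant who meets both. With about 12 participants, one label visibly moves a reported percentage.

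**Working it through.** The plan gives no figure on this point to reproduce: "No formal hypothesis testing is planned", and "The sample size for this study was selected based on feasibility". The check is date arithmetic and a full listing of result patterns.

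**Inputs.** ADA days 1, 150, 330, 510 and 720 (Protocol Table 8-1). Two samples on Day 1 (Protocol 8.4.1.1). Cut-off 16 × 7 = 112 days (SAP 2.7.6). Arm sizes from "Approximately 12 participants who meet the inclusion/exclusion criteria will be randomized in a 2:1 ratio", so about 8 and 4.

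**Step 1: status of the 4-hour sample.** SAP 2.7.3 makes the pre-injection sample the ADA baseline. The 4-hour sample follows the first dose, so it is post-baseline under SAP 2.1.1. That gives post-baseline samples at 4 hours and Days 150, 330, 510 and 720 (five), or three in Part 1.

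**Step 2: gaps between scheduled ADA days.**
- 150 − 1 = 149 days (21.3 weeks)
- 330 − 150 = 180 days (25.7 weeks)
- 510 − 330 = 180 days (25.7 weeks)
- 720 − 510 = 210 days (30.0 weeks)

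All exceed 112. The narrowest margin is 149 − 112 = 37 days, so modest visit slippage does not change this. Neither under-16-week clause applies to any scheduled pattern, and any two scheduled positives are persistent.

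**Step 3: what transient can mean.** For one isolated positive, the distance between the neighbouring negatives is:
- Day 150: 330 − 1 = 329 days (47.0 weeks)
- Day 330: 510 − 150 = 360 days (51.4 weeks)
- Day 510: 720 − 330 = 390 days (55.7 weeks)

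The true positive period could lie anywhere within these limits.

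**Step 4: all patterns for a baseline-negative participant, with the 4-hour sample as a time point of its own.** Patterns with at least one positive: 2^5 − 1 = 31 for the full study and 2^3 − 1 = 7 for Part 1. If the last-negative condition governs both transient clauses, the full study splits into 27 persistent and 4 transient, and Part 1 into 5 and 2. No pattern falls in both classes or in neither.

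**Step 5: drop the 4-hour sample.** Of the 2^4 = 16 full-study patterns with a positive 4-hour sample, 4 change class:

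| Positive at | With 4-hour sample | Without it |
|---|---|---|
| 4 h only | treatment-induced, transient | not treatment-induced |
| 4 h and Day 150 | persistent | transient |
| 4 h and Day 330 | persistent | transient |
| 4 h and Day 510 | persistent | transient |

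In Part 1, 2 of 2^2 = 4 change: 4 h only, and 4 h with Day 150.

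**Step 6: overlap.** If the last-negative condition governs only the second transient clause, one scheduled pattern is in both classes: positive at the last sample alone (Day 720, or Day 330 in Part 1). Off schedule, take a positive at Day 330 and a negative early-exit sample on Day 400. The gap is 400 − 330 = 70 days (10 weeks), under 112. This meets the third persistent clause and the first transient clause under either reading. Protocol Section 8 asks for an end-of-study visit as soon as possible after early discontinuation, and the end-of-study column of Table 8-1 includes ADA, so such a sample can arise. The example uses actual dates. If Day 360 had been attended, SAP Table 2-1 would map this exit to Day 450, giving 450 − 330 = 120 days and no overlap. SAP 2.7.6 does not say which applies.

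**Step 7: size.** One participant is 1/8 = 12.5 points of the inclisiran arm or 1/4 = 25 points of the placebo arm.

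**The case against.** The SAP nowhere says expressly that the 4-hour sample counts; this comes from applying general definitions. The text of the Table 8-1 footnote on the ADA row was not in the copy read, and SAP 2.7.6 leaves further detail to a separate ADA report. ADA is summarised descriptively with a listing, so among about 12 participants an isolated 4-hour positive would be seen. These points limit the importance. They do not remove the rule, because the tabulated categories follow the SAP definitions as they stand.

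Several stronger readings are tempting but not supported:
- *The schedule cannot test the 16-week cut-off.* Two scheduled positives do show a separation of at least 16 weeks. What the schedule cannot show is a duration below that.
- *The classes overlap because of the sample spacing or the 4-hour sample.* On scheduled visits 0 of 31 patterns overlap under the natural reading. The overlap comes from wording and off-schedule samples.
- *A participant positive only at Day 330 moves from persistent at the Part 1 analysis to transient at the end with nothing new.* The negatives at Days 510 and 720 are new data.
- *Apheresis between the two Day 1 samples makes them non-comparable for ADA, or a 4-hour positive must be drug interference.* Neither document says so.

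**Conclusion.** The point holds as a defect of definition. Under SAP 2.1.1, 2.7.3 and 2.7.6 a positive 4-hour sample after a negative pre-dose sample is treatment-induced ADA, and it converts an isolated positive at Day 150, 330 or 510 from transient to persistent. A smaller gap is the double classification of a single positive less than 16 weeks before a negative last sample. The label transient also needs a caveat on this schedule.

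The conclusion rests on three assumptions: the 4-hour sample is its own time point, its positive result is confirmed where the persistent definition requires that, and antibody cannot plausibly be induced within 4 hours. The last is an immunological premise that the documents do not state. They also give no assay false-positive rate, so how often this would occur cannot be sized. The consequence is about 12.5 or 25 percentage points per affected participant in one descriptive safety table. The primary endpoint is not affected.

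**What to change.** In SAP 2.7.6:

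1. Define ADA baseline as the Day 1 pre-injection sample. Exclude the 4-hour sample from the treatment-induced, transient and persistent derivations, and list it beside the pre-dose result.
2. State that the last-sample-negative condition applies to both transient clauses. Count a single positive less than 16 weeks before a negative last sample in one class only, with a stated precedence, and say whether intervals use actual sample dates or mapped visit days.
3. Add a note that on this schedule transient means one isolated positive visit and does not establish a duration under 16 weeks.

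The cost is wording and programming only; no sample or visit changes. The 16-week convention can stay, since replacing it would be a matter of preference. A separate instruction to re-derive the classes at the end adds little, because a Part 2 analysis is already planned.

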2.7.7 Other safety evaluation

Shift from baseline in Tanner stage will be summarized by sex, treatment, visit and Part. Additionally, shift in menarche status from baseline will be summarized by visit and treatment group and Part. Mean and SD of age of the participants in each of category of shift table will be provided. Listing will be provided.

In cases where following a Tanner stage 5 assessment the data of the next visit are missing, they will be imputed as Tanner stage 5 (as the protocol does not mandate to repeat the Tanner stage assessment once Tanner stage 5 has been reached). Similarly, missing menarche data will be imputed to yes if the previous assessment was yes for menarche.

[REDACTED]

2.9 Biomarkers

[figure not shown]
Analyses of PCSK9 and lipids/lipoproteins are discussed in [Section 2.6](#). No additional biomarkers will be evaluated in this study.

[REDACTED]

2.11 Interim analysis

Interim analyses are planned for the monitoring of participants' safety and will be performed as determined by the DMC (see DMC charter). Interim safety analyses before the unblinding for the analysis of Part 1 of the study will be performed by an independent statistician/programmer who will not be involved in the trial conduct. The interim results will be reviewed by the independent DMC.

3 Sample size calculation

The sample size for this study was selected based on feasibility.

4 Change to protocol specified analyses

No change from protocol specified analysis was made.

5 Appendix

5.1 Imputation rules

5.1.1 Study drug

Missing/partial start date or end date of treatment will not be imputed.

5.1.2 AE date imputation

Partial AE start and end dates will be imputed. If there is uncertainty whether an AE occurred on-treatment or not, imputation will be performed, such that AE will be considered as on-treatment. Rules for imputing AE end date or start date will be provided in Programming Dataset Specification (PDS) document in details.

5.1.3 Concomitant medication date imputation

Rules for imputing the CM end date or start date will be provided in Programming Dataset Specification (PDS) document in details.

5.2 AEs coding/grading

The MedDRA version which will be available at the time of database lock, will be used for the coding purpose of the adverse events.

5.3 Analyses to be performed in Part 1 analysis (ANA1) and Part 2 analysis (ANA2)

	Data to be included (ANA1 and ANA2 analysis)			Comment
	Part 1	Part 2	Overall: Part 1 & Part 2 combined	
Disposition	ANA1	ANA2		
Protocol Deviations	ANA1	ANA2		
Demography and baseline characteristics	ANA1			
Medical History	ANA1			
Prior therapies (Including lipid modifying therapy)	ANA1			
Concomitant therapies**	ANA1	ANA2		SAF for ANA1;

Novartis SAP amendment 4	For business use only			Page 33 CKJX839C12302
(Including lipid modifying therapy [REDACTED])				OAS for ANA2. CM will be counted in both parts when starting from part 1 and continuing to part 2
Doses, Duration on study, Exposure	ANA1	ANA2	For exposure	
Efficacy (Primary endpoint & secondary endpoints)	ANA1			
Efficacy (secondary endpoints)	ANA1	ANA2	For some selected efficacy parameters	
AEs**	ANA1	ANA2		SAF for ANA1; OAS for ANA2.
Diabetes assessment	ANA1	ANA2		SAF for ANA1 ; OAS for ANA2.
Lab and Vital signs	ANA1	ANA2		SAF for ANA1 ; OAS for ANA2.

5.4 Search criteria for other safety topics

The most recent eCRS available during database lock will be used.

5.5 Laboratory parameters derivations

The following table shows the criteria for clinically notable laboratory values. Not all parameters have notable criteria defined:

Table 5-1 Clinical notable criteria for selected laboratory tests

	Notable post-baseline value
Hematology	
Hemoglobin	≤ 10 g/dL
Hematocrit	$\leq 0.8 \times LLN$
WBC count / Leukocytes	$\leq 2.8 \times 10^9/L$ or $\geq 16 \times 10^9/L$
Platelet count	$\leq 75 \times 10^9/L$ or $\geq 700 \times 10^9/L$
Clinical chemistry	
C(P)K	$>5 \times ULN$ >5 and $\leq 10 \times ULN$ >10 and $\leq 20 \times ULN$ $>20 \times ULN$
Creatinine	$\geq 50\%$ increase from baseline (not >2 mg/dL) >2 mg/dL $\geq 50\%$ increase from baseline or >2 mg/dL
eGFR	<30 mL/min/1.73m ² ≥ 30 to <60 mL/min/1.73m ² ≥ 60 to <90 mL/min/1.73m ²
Glucose	≥ 100 to <126 mg/dL ≥ 126 mg/dL
HbA1C	$\geq 5.7\%$ to $<6.5\%$ $\geq 6.5\%$

Table 5-2 Notable liver function test values

Criterion
ALT $> 3 \times$ the upper limit of normal range (ULN)
ALT $> 5 \times$ ULN
ALT $> 8 \times$ ULN
ALT $> 10 \times$ ULN
ALT $> 20 \times$ ULN
AST $> 3 \times$ ULN
AST $> 5 \times$ ULN
AST $> 8 \times$ ULN
AST $> 10 \times$ ULN
AST $> 20 \times$ ULN

ALT or AST > 3 x ULN
ALT or AST > 5 x ULN
ALT or AST > 8 x ULN
ALT or AST > 10 x ULN
ALT or AST > 20 x ULN
Total bilirubin > 2 x ULN
TBL >2xULN & DBL >ULN
TBL >2xULN & DBL >2xULN
ALP > 2 x ULN
ALT or AST > 3 x ULN and total bilirubin > 2 x ULN
ALT or AST > 5 x ULN and total bilirubin > 2 x ULN
ALT or AST > 8 x ULN and total bilirubin > 2 x ULN
ALT or AST > 10 x ULN and total bilirubin > 2 x ULN
ALT or AST > 20 x ULN and total bilirubin > 2 x ULN
ALT or AST > 3 x ULN and Total Bilirubin > 2 x ULN and ALP < 2 x ULN (Hy's law)

ALT = alanine aminotransferase, AST = aspartate aminotransferase, ALP = alkaline phosphatase

When a criterion contains multiple laboratory parameters, the criterion will only be considered to have been met when all conditions occur within a 3-day window.

5.6 Vital signs – definition of clinically notable values

The following table show the clinical notable criteria for vital signs.

Table 5-3 Clinical notable criteria for vital signs

Age	SBP [mmHg]	DBP [mmHg]	HR [min^{-1}]
≥ 12 years	< 90, > 145	< 55, > 90	< 45, > 95

5.7 Statistical models

No additional details to be discussed.

5.8 Rule of exclusion criteria of analysis sets

The protocol deviations (PD) and other criteria leading to complete exclusion from analyses sets will be included in this section and will be finalized before study DBL.

6 Reference

